#### **6.2.2 Baseline (within 30 days of index ablation procedure)**

- Inclusion/Exclusion criteria
- Demographic information (Age, Sex, Race, Ethnicity)
- Review of Medical and Cardiac history, including AF history
- Documentation of AF classification (Persistent or Longstanding Persistent)
- Vital History (Height, Weight, BMI, Blood Pressure, Heart Rate)
- NYHA Classification
- Heart Rhythm Assessment using 12 Lead ECG, if done
- ECHO (TTE) within 90 days of the procedure, if done
- Medications history – Antiarrhythmic drugs (AADs), anticoagulants including previous AAD treatment failures. Medication information should include:
  - Name and indication
  - Dosage with units and frequency
  - Start and stop dates

**6.2.3 Surgical Procedure**

- Evaluation of adverse events (AEs)/SAEs
- Cox-Maze III
- Con-concomitant surgical procedure
- Post-procedure heart rhythm assessment using 12 lead ECG, if done
- Cardioversion history, if applicable

**6.2.4 Pre-Discharge**

- Evaluation of any AEs/SAEs
- Heart Rhythm Assessment using 12 lead ECG, if done
- Medications – class I and III AAD's and anticoagulants, including any adjustments
- Cardioversion history since procedure

Medication review \*Note: Medications administered during the post-operative period do not need to be captured in the eCRF.

**6.2.5 30-days Post-Procedure (+/- 7 days)**

- NYHA Classification
- Heart Rhythm Assessment using 12 lead ECG, if done
- Evaluation of any AEs/SAEs
- Medications – class I and III AAD's and anticoagulants, including any adjustments
- Review cardioversion since last visit

**6.2.6 Study Exit**

Once study subjects have completed their last follow-up visit, and 24-Hr rhythm assessment has been obtained, the subject will be exited from the study.

**6.2.7 Unscheduled Visit(s)**

An unscheduled visit is defined as a visit that occurs outside of the defined visit windows. Subjects reporting symptoms of AF/AFL/AT prior to their last follow-up visit, should contact their site for an in-clinic or remote evaluation. The following will be conducted/collected at the visit:

- Heart Rhythm Assessment using 12 lead ECG or equivalent per standard of care, if done
- Any AF treatment that was needed
- Evaluation of any AEs/SAEs
- Medications – class I and III AADs and anticoagulants, including any adjustments

## 6.2.8 Schedule of Events

Trial Activity	Visit 1	Visit 2	Visit 3	Visit 4	Visit 5	
	Baseline (Within 30 days of index procedure)	Procedure	Pre-Discharge	30-days (Within 23-37 days of index procedure)	12-months (≥ 12-months but ≤ 24-months of index ablation procedure)	Unscheduled visit
Informed consent & Inclusion/Exclusion	X					
Demographics	X					
Medical/Surgical History	X					
AF Classification	X					
Vital History	X					
NYHA Classification	X			X	X	X
12 Lead ECG, if done 	X	X	X	X		X
Medications/AAD Adjustment Review 	X		X	X	X	X
Adverse Events (AEs/SAEs)		X	X	X	X	X
Echocardiogram (transthoracic), if done	X					
Cox Maze III		X				
Concomitant Surgical Procedure		X				
Cardioversion Review 		X	X	X	X	X
24-Hours Holter (or equivalent)					X	

 12-lead ECG performed will need to be 30 seconds in length.

 Class I/III AADs and/or OACs only

 At physician's discretion and per institutions Standard of Care (SOC).

### **6.3 Requirement for Clinical Laboratories**

An independent core laboratory will be utilized for assessment of the following data collected on subjects:

- 24-Hour rhythm monitoring recordings

All monitoring shall be performed in accordance with the core laboratory's recommended protocol.

## **7 ADVERSE EVENTS**

Safety data for the primary safety endpoint will be collected from the start of the index ablation procedure to 30-days post procedure. The primary safety endpoint will be an evaluation of the incidence of major adverse events (MAEs) listed in section 4.1 for the procedural to 30-day post procedure time period. Deaths beyond 30-days or through last follow-up that are attributed to the surgical ablation procedure or CRYOF would be reported as MAEs.

### **7.1 Definition**

#### **7.1.1 Major Adverse Event**

Events qualifying as MAEs as defined in section 4.1 include:

- Excessive bleeding
- Myocardial Infarction (MI)
- Stroke, TIA
- Death

Any condition that was recorded as pre-existing is not a MAE unless there is a change in the nature, severity, or degree of the condition.

Sick Sinus Syndrome (SSS) and the implantation of a pacemaker for treatment of SSS post procedure will not be recorded as a MAE since it is a known underlying condition for subjects with long-standing persistent AF undergoing cardiac coagulation procedures.

#### **7.1.2 Adverse Event**

Adverse Event (AE) is defined as any undesirable clinical occurrence or change from subject's baseline (or pre-device procedure) condition, whether it is considered device related or not. An AE is also defined by the International Organization for Standardization (ISO) as an untoward medical occurrence, unintended disease or injury, or untoward clinical signs (including abnormal laboratory findings) in subjects, users or other persons, whether or not related to the investigational medical device and whether anticipated or unanticipated.

Adverse Event Identification: a condition that is one of the following:

1. A unique symptom or event that is a change from the subject's baseline status.
2. A series of symptoms or events that can be categorized as a single entity based on definitions found herein.
3. A specific diagnosis responsible for a clinical change.
4. A worsening or exacerbation of a pre-existing condition.

### 7.1.3 Serious Adverse Event

If the AE meets any of the criteria below, it is regarded as a Serious Adverse Event (SAE).

- a) Led to a death,
- b) Led to a serious deterioration in health of the subject, that either resulted in
  1. Life-threatening illness or injury, or
  2. Hospitalization (initial or prolonged) or
  3. Disability or permanent impairment of a body structure or a body function
  4. Congenital anomaly (physical or mental)/birth defect/fetal distress/fetal death
  5. Chronic disease
  6. Medical or surgical intervention to prevent life-threatening illness or injury or permanent impairment to a body structure or a body function
- c) Other Serious (important Medical Events).

**Note:** A planned hospitalization for pre-existing condition, or a procedure required by the protocol, without a serious deterioration in health, is not considered to be an SAE.

Note: "Death" should not be reported as an adverse event. The cause of death should be reported as an adverse event. The only exception is "Sudden Death" when the cause is unknown.

### 7.1.4 Device Deficiency/Device Malfunction

Device Deficiency is defined as an inadequacy of a medical device related to its identity, quality, usability, durability, reliability, safety or performance, such as malfunction, misuse or use error and inadequate labeling. This includes the failure of the device to meet its performance specifications or otherwise perform as intended. Note: Performance specifications include all claims made in the labeling of the device.

A device malfunction is the failure of a device to meet its performance specifications or otherwise perform as intended.

All device deficiencies of the CRYOF device shall be documented throughout the clinical investigation and managed by the sponsor in accordance with written procedures for the control of a non-conforming product. The sponsor shall take, where applicable, appropriate corrective and preventative actions to protect the safety of subjects, users, and other persons. Device deficiencies of the comparator, if applicable, shall be documented. Where applicable, the analysis of used or explanted investigational devices shall be included as supportive information.

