#### **2.2.4 Device Handling**

Subjects enrolled in this study will already have been treated, therefore device accountability is not required.

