### **6.2 Follow-up Assessments**

#### **6.2.1 12-Month Visit ( $\geq$ 12-months but $\leq$ 24-months post index ablation procedure)**

Subjects will be consented 12 to 24 months post procedure and will be provided with a 24-Hour rhythm monitoring device at that time. The post procedure follow-up assessment will include:

- NYHA Classification
- 24-Hr Rhythm Assessment
- Evaluation of AEs/SAEs
- Medications – class I and III AAD's and anticoagulants, including any adjustments
- Review cardioversion since last visit

Note: If a clinical site is capable of remote subject visits, a modified visit assessment may be conducted. Remote subject visits should include Telemedicine appointments with the Investigator, where feasible, to allow direct engagement with the study subject and to ensure complete data collection. Rhythm monitoring devices may be provided to the subject either during an in-clinic follow-up visit, or shipped to the subject for a remote follow-up visit as applicable.

If clinical site is NOT able to perform remote subject visits, an attempt will be made to schedule the study subject visit as close to the visit window as is possible.

Regardless of when the subject is consented, the following data will be collected by reviewing the subjects' medical records retrospectively. For retrospective visits that fall outside of the required windows, please refer to sections 6.2.9 (Unscheduled Visit) and 10.6 (Protocol Deviations).

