### **7.5 Adverse Event and Device Deficiency/Device Malfunction Reporting**

#### **7.5.1 AE/ADE/UADE Reporting**

##### General AE Reporting

Safety surveillance and reporting starts as soon as the subject is enrolled in the clinical investigation. Safety surveillance and reporting will continue until the 12-Month follow-up visit has been performed, the subject is deceased, the subject concludes participation in the clinical investigation, or the subject withdraws from the clinical investigation. All adverse event data, including deaths and device deficiency data, will be collected throughout the time period defined above and will be reported to the Sponsor on a CRF. Additional information with regard to an adverse event should be updated within the appropriate CRF.

Except for those events listed in Section 7.6, AEs potentially related to the study procedure or AtriCure devices used in the study and other AEs that the PI determines as critical to safety evaluation will be captured on the eCRF. Standard medical terminology should be used when recording AEs.

In addition, the following information should be recorded:

- Onset Date
- Resolution date or date of death
- Intensity of the event
- Action Taken
- Outcome of the event
- Relationship of AE
- Indication of whether the event is serious

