### **7.5.3 Device Deficiency/Malfunction Reporting**

All device deficiencies/malfunctions should be reported on the appropriate CRF.

The investigator should report all device deficiencies/malfunctions to the Sponsor as soon as possible but no later than outlined below.

Clinical Sites	Reporting timelines
All Sites	Device deficiencies/malfunctions must be reported to the Sponsor no later than 10 calendar days from the day the site personnel became aware of the event or as per the investigative site's local requirements, if the requirement is more stringent than those outlined.

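### Device-deficiency collection is tied to a window that opens after CRYOF was used, and the chart review never asks about it, so under-ascertainment is likely (minor)

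*Combined protocol and SAP*

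**What the plan says.** **When the device was used.** Section 2.2.4 states: "Subjects enrolled in this study will already have been treated, therefore device accountability is not required". Section 6.2.1 adds: "Subjects will be consented 12 to 24 months post procedure and will be provided with a 24-Hour rhythm monitoring device at that time". Baseline, procedure, discharge and 30-day data are then abstracted from the medical record.

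**When deficiencies are collected.** Section 7.1.4 says: "All device deficiencies of the CRYOF device shall be documented throughout the clinical investigation". Section 7.5.1 defines the period more narrowly: "Safety surveillance and reporting starts as soon as the subject is enrolled in the clinical investigation". It continues: "All adverse event data, including deaths and device deficiency data, will be collected throughout the time period defined above".

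**What the chart review asks for.** Section 6.2.3 lists adverse events, the Cox-Maze III, the concomitant operation, an ECG item ("Post-procedure heart rhythm assessment using 12 lead ECG, if done") and cardioversion. The Schedule of Events (6.2.8) has an adverse-event row at the procedure visit. It has no row at any visit for deficiencies, malfunctions or complaints.

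**Other reporting routes.** Section 7.5.3 wants all deficiencies on a CRF and sets a deadline: "Device deficiencies/malfunctions must be reported to the Sponsor no later than 10 calendar days from the day the site personnel became aware". Section 3 has the principal investigator report quality problems, malfunctions and user errors for devices used in the procedure. Sections 7.7.1 and 7.7.2 require reported malfunctions to be entered in the EDC, and 7.7.2 names a device observation form. Section 15.5 says all deficiencies go to the sponsor.

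**The concern.** A probe can malfunction only while it is in use. Here that means the index operation, which precedes enrollment in every subject. A collection period that starts at enrollment therefore leaves out the whole period at risk. The retrospective review could have made up for this, but its item list does not mention deficiencies.

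The adverse-event item is not a substitute. Section 7.1.2 defines an adverse event as an undesirable clinical occurrence. Section 7.1.4 defines a deficiency as an inadequacy of the device, whether or not the patient was harmed. A probe that failed and was replaced without consequence falls under the second definition only.

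The primary objective is the safety and performance of CRYOF, and Section 1.1.5 says the data are meant for regulators in Europe, China and elsewhere. If few or no deficiencies are reported, a reader could not tell a reliable device from a question that was not asked.

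**Working it through.** The protocol states no expected deficiency count or rate, so there is no planned figure to reproduce. The check is mainly of the text.

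**Step 1. Set the time windows side by side.**

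| Source | Period or trigger | Includes the index operation? |
|---|---|---|
| 2.2.4, 6.2.1 | Device used before enrollment; consent 12 to 24 months later | This is the period at risk |
| 7.5.1 | From enrollment; deficiency data named | No, read literally |
| 7.1.4 | During the investigation; no start stated | Unclear |
| 7 (introduction) | Primary safety data from the start of the procedure | Yes, but deficiencies not mentioned |
| 6.2.3, 6.2.8 | Adverse events at the procedure visit | Yes, but no deficiency item |
| 3 | Problems with devices used in the procedure | Intended, though worded as use during the study |
| 7.5.3 | Deadline runs from site awareness | Not excluded |
| 7.7.1, 7.7.2 | Reported malfunctions entered in the EDC within 10 days of observation | Not excluded |

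The enrollment start in 7.5.1 is inconsistent with the introduction to Section 7, with 6.2.3 and with the intent of Section 3.

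**Step 2. Look for a prompt.** The routes in 3, 7.5.3, 7.7.1, 7.7.2 and 15.5 create a duty once someone notices a deficiency. None tells the chart abstractor to look for one.

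**Step 3. Illustrate what incomplete capture does.** Let n = 150 (Section 5.6), t the true deficiency rate and c the share captured. Both t and c are assumptions; the documents give neither.

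Expected reports = 150 × t × c, and P(none reported) = (1 − t × c)^150.

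| Assumed t | c = 0 | c = 10% | c = 25% | c = 50% | c = 100% |
|---|---|---|---|---|---|
| 1% | 0; 100% | 0.15; 86% | 0.38; 69% | 0.75; 47% | 1.5; 22% |
| 2% | 0; 100% | 0.3; 74% | 0.75; 47% | 1.5; 22% | 3.0; 5% |
| 5% | 0; 100% | 0.75; 47% | 1.9; 15% | 3.75; 2% | 7.5; 0.05% |

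Each cell gives expected reports, then the chance of none.

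Taken at face value, 0 of 150 has a one-sided 95% upper bound of 1 − 0.05^(1/150) = 2.0%. That bound is valid only at c = 100%. With t = 2%, a zero count has probability 5% under full capture and 47% under 25% capture. At t = 1%, zero occurs 22% of the time even with perfect collection.

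**Step 4. Check reach into the endpoints.** Deficiency is not among the primary or secondary endpoints in Section 4. The tests in 8.2, the sample size in 8.3 and the success criteria in 8.10 do not use it.

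**The case against.** A reader might infer that the study will report almost no deficiencies by construction. The documents do not support that. It follows only from 7.5.1 read literally and alone, the c = 0 column above. Sections 3, 7.5.3, 7.7.1, 7.7.2 and 15.5 contain no explicit exclusion of the index operation, so a malfunction found in an operative record could be reported.

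A reader might also infer that the 10-day deadline has already passed for any intra-operative malfunction. Awareness can mean discovery at chart review, and a missed deadline makes a report late without cancelling the duty. The ambiguity stands; the stronger inference does not.

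Other parts of the defense also have force:

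- The CRFs are not in the documents, and deficiencies may have an event-driven form, so a missing schedule row is limited evidence.
- Clinical consequences are partly captured. Adverse events are reviewed at the procedure visit with attribution to the device, and Section 3.1 records the lesions actually made when the set is incomplete. It would be too strong to say malfunctions cannot be linked to performance failures. A recorded omission can be linked; its cause may be missing.
- Moving the start date in 7.5.1 to the procedure would bring deficiencies into the window, because that section names them. What would remain is the missing prompt.
- The rates in the illustration are assumed, and no section plans a deficiency rate or a claim based on zero events.

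These points limit the size of the problem. They do not remove the conflict between windows or supply a prompt.

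**Conclusion.** Wrong as written, and minor. The window in 7.5.1 excludes the only time CRYOF was in use and conflicts with other sections, and the chart review does not ask for deficiencies. The result is unprompted capture that depends on records 12 to 24 months old, with likely under-ascertainment of unknown size. A low or zero count could not be taken as evidence of reliability.

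The size cannot be derived from the documents; the 0-of-150 figures are illustrative and rest on assumed rates and capture. Both hypothesis tests, power and sample size are unchanged.

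One limitation would remain in any case. Inclusion criterion 3 (5.3.2.1) requires the listed left atrial and coronary sinus lesions, so a patient in whom a malfunction left one of them undone is not eligible and cannot appear in any deficiency count.

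**What to change.** 1. State in 7.1.4 and 7.5.1 that deficiency collection runs from the start of the index procedure, by retrospective record review. Reconcile Sections 3, 7.1.4, 7.5.1 and 7.5.3 to that.
2. Add to 6.2.3 and to the Visit 2 column of 6.2.8: *CRYOF deficiency or malfunction during the index procedure: yes / no / not documented, with description and lesion affected.* Check the answers against the complaint records the sponsor already holds.
3. Report the count over subjects with adequate documentation, and show the not-documented number separately.
4. Clarify that the 10-day clock in 7.5.3 runs from the later of enrollment and site awareness.
5. Note the selection through inclusion criterion 3 as a limitation when the count is reported.

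The cost is one CRF item per subject, one schedule row and a complaint-file check. The charts are already being reviewed, so no visits are added.

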## 7.2 Pre-Existing Conditions Versus Adverse Events

A pre-existing condition is defined as a medical condition that is present before the index ablation procedure and is to be reported as part of the subject's medical history. It must be reported as a new AE if the intensity, frequency, or the character of the condition worsens during the study treatment and the AE was determined to have the relationship to the study procedures and/or study devices.

To avoid confusing pre-existing conditions with AEs during data analysis, the study sites must make all attempts to provide start dates for all baseline medical conditions. Any pre-existing condition that now meets the stated criteria as an AE should be recorded on the AE CRF as an exacerbation of the pre-existing condition and the start date will be recorded as the time when the exacerbation occurred.

### 7.3 Severity of Adverse Events

It is the Investigator's responsibility to assess the severity of an AE. A change in severity may constitute a new reportable AE.

The following guideline should be used to determine the severity of each adverse event:

- **MILD:** Awareness of experience, but easily tolerated. No medical intervention required
- **MODERATE:** Enough discomfort to interfere with usual activities. Medical intervention required
- **SEVERE:** Inability to carry out usual activities. Medical/surgical intervention (including hospitalization or prolongation of hospitalization) required.

### 7.4 Device Relationship

Determination of whether there is a reasonable possibility that an investigational product or device under investigation caused or contributed to an AE is to be determined by the Investigator and recorded on the appropriate CRF form. Determination should be based on assessment of temporal relationships, evidence of alternative etiology, medical/biologic plausibility, and subject condition (pre-existing condition).

It is the Investigator's responsibility to assess the relationship of an AE to the study procedure and/or device.

Adverse events will be assigned an attribution according to the Investigator's believed primary cause. Events will be categorized by relationship to the investigational device(s) listed in this protocol or ancillary device, surgical ablation procedure, general cardiac surgical procedure or subsequent intervention, concomitant medications, pre-existing condition, intercurrent condition, intercurrent intervention, or unknown.

The following guidelines should be used in determining the relationship of an adverse event to the study device or procedure:

- **Unknown:** A clinical event (including abnormal laboratory result) that cannot be determined to be related or unrelated to device/procedure/drug given information provided.
- **Device Related Adverse Event:** An adverse event, that in the judgment of the Investigator, resulted from use of the cryoICE® cryoablation system may have caused or contributed to the AE.
- **Procedure Related Adverse Event:** An adverse event which, in the judgment of the Investigator, results as a consequence of the investigational procedure and is not specifically related to the use of the cryoICE® cryoablation system.
- **General Surgery Related Adverse Event:** An adverse event which, in the judgement of the Investigator, results as a consequence of general cardiac surgical procedural complications and/or subsequent interventions.
- **Concomitant Medication-Related Adverse Event:** An adverse event is considered to be concomitant medication related when, in the judgment of the Investigator, it is reasonable to believe that the event is associated with concomitant medications used in conjunction with the investigational device and is not otherwise specific to the investigational device (e.g. bleeding associated with anticoagulation medication).
- **Intercurrent Condition:** It is reasonable to believe that the event is directly associated with an intercurrent condition/co-morbidity.
- **Intercurrent Intervention:** It is reasonable to believe that the event is directly associated with an intercurrent intervention which was performed for reasons other than to address a

device or ablation/general cardiac surgical procedure related complication.

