#### **10.8.3 Independent Physician Adjudicator (IPA)**

An independent, non-investigator physician(s) will function as the adjudicator(s) under the direction of AtriCure, Inc. The physician(s) will be responsible for the review and adjudication of reported adverse events occurring up to 12-months post-procedure, including:

1. All Major Adverse Events listed under the primary safety endpoint;
2. All Serious Adverse Events;
3. All Unanticipated Device Effects;
4. All Adverse Events that are potentially related to the procedure or any of the AtriCure devices used in the study.

In addition, all primary safety endpoints and other adverse events determined by the adjudicator(s) to be relevant, will be adjudicated until the subject exits the study.

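### Section 7.4 asks no contributory question for the ablation procedure, and Section 7.5.1 lets the investigator decide which non-serious candidate MAEs are entered, so some may never reach the adjudicator

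*Combined protocol and SAP*

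**What the plan says.** **Attribution (protocol Section 7.4).** The section opens with a contributory question about the product: whether the "device under investigation caused or contributed to an AE is to be determined by the Investigator and recorded on the appropriate CRF form". It then states: "Adverse events will be assigned an attribution according to the Investigator's believed primary cause". The categories include the device, the surgical ablation procedure, general cardiac surgery and concomitant medication. The device category keeps contributory wording. The procedure category covers an event that "results as a consequence of the investigational procedure and is not specifically related to the use of the cryoICE® cryoablation system", and the general surgery category an event that "results as a consequence of general cardiac surgical procedural complications and/or subsequent interventions". Neither of these two mentions contribution.

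**Entry on the eCRF (Section 7.5.1).** Apart from the expected events listed in Section 7.6, what is captured is "AEs potentially related to the study procedure or AtriCure devices used in the study and other AEs that the PI determines as critical" for judging safety. The preceding paragraph of the same section says that all adverse event data are collected and reported on a CRF.

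**Serious events (Section 7.5.2).** All SAEs go to the sponsor, with no relatedness condition.

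**Adjudication (Section 10.8.3 and synopsis).** The independent physician reviews reported events: all MAEs, all SAEs, all unanticipated device effects and "All Adverse Events that are potentially related to the procedure or any of the AtriCure devices used in the study". The synopsis says that this review covers severity and relatedness.

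**Endpoints.** The Section 4.1 composite is limited to events related to the surgical ablation procedure. Section 4.3 counts SAEs related to the device or the ablation procedure.

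**The concern.** Inclusion criterion 4 (Section 5.3.2.1) requires a concomitant valve, coronary or septal-defect operation on bypass. Every event around the operation therefore has at least two candidate procedural causes. For the device, a contributing role is asked about. For the ablation procedure, which defines the primary composite, it is not; the form takes the cause that the investigator believes to be the main one. The principal investigators are cardiac surgeons (Section 3).

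Investigator judgement also decides whether a non-serious event is entered at all. An independent adjudicator can overrule a site on an event that was reported, but cannot add one that was not. Section 4.1 relies on adjudication to keep the primary safety endpoint objective. For non-serious events that could qualify as MAEs, the documents do not secure this.

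**Working it through.** **1. Which events can be missed?**

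| Event type | Must it be entered? | Does the adjudicator see it? |
|---|---|---|
| SAE, any attribution | Yes (7.5.2) | Yes (10.8.3), for relatedness too (synopsis) |
| Non-serious, site finds it potentially related or critical | Yes (7.5.1) | If potentially related or an MAE, yes (10.8.3) |
| Non-serious, site finds it neither | Not under the restrictive sentence of 7.5.1; yes under the broader one | Only if reported |

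The third row is the gap.

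**2. Can an event in the third row belong to the primary endpoint?** Section 7.1.1 introduces its list with "Events qualifying as MAEs as defined in section 4.1 include". Its bleeding item refers back to Section 4.1, which needs an injury related to the device or study procedure, plus either a transfusion or a hematocrit fall of at least 20%. Neither seriousness nor a minimum number of units is required. A transfused bleed that the site puts down to the valve or coronary operation can therefore stay off the eCRF, although an adjudicator might have found it related to the ablation. Section 7.6 adds to this: within 48 hours, certain hematocrit decreases that need fewer than 2 units of red cells are kept off the eCRF.

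**3. The plan's own figures.** Inputs from Sections 8.2.2 and 8.3: n = 150, performance goal 15%, expected rate 8.5%, exact binomial test at one-sided α = 0.05, pass at 15 or fewer subjects with an MAE.

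- Level: P(X ≤ 15 | 150, 0.15) = 0.0493. With 16 allowed it would be 0.0807, so 15 is the correct limit.
- Power: P(X ≤ 15 | 150, 0.085) = 0.794, against 80% stated.

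Both are reproduced.

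**4. Sensitivity to unentered events.** Let d be the share of all subjects who have a true MAE that is never entered. The counted rate is 0.15 − d, and the chance of passing is P(X ≤ 15 | 150, 0.15 − d).

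| d (assumed) | Expected counted MAE subjects | Chance of passing at a true 15% |
|---|---|---|
| 0 | 150 × 0.15 = 22.5 | 4.9% |
| 1% | 150 × 0.14 = 21.0 | 9.4% |
| 2% | 150 × 0.13 = 19.5 | 16.6% |

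A loss of 1 to 2 points out of 15 is 1/15 = 6.7% to 2/15 = 13.3% of subjects with an MAE. Expressed as a fraction of those subjects, a loss of 5%, 10% or 20% gives counted rates of 14.25%, 13.5% and 12%, and passing chances of 8.0%, 12.6% and 27.1%.

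These are upper bounds for the assumed shares. They require that every unentered event would have been adjudicated as qualifying and that it occurred in a subject with no other counted MAE.

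**The case against.** The other side has substantial points, and most of them narrow the concern.

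- **SAEs are covered.** They are reported and adjudicated for relatedness whatever the site believes. A reader might infer that the secondary endpoint of related SAEs is biased low by the attribution rule itself. The documents do not support that: nothing says this endpoint uses the site's attribution over the adjudicator's. Nor do they say the reverse, which is why the fix asks for a statement.
- **Device contribution is asked.** One might read the primary-cause sentence as cancelling the contributory question. Section 7.4 does not say so, and does not expressly allow only one category. What is missing is that question for the ablation procedure.
- **The entry test is wider than primary cause.** An event filed mainly under general surgery can still be potentially related and so be entered. There is also the second route for events judged critical, and the broader sentence on collecting all adverse event data. Loss is a risk, not a certainty, and the two sentences of Section 7.5.1 are in conflict.
- **Few MAE types can be non-serious.** A myocardial infarction as Section 4.1 describes it would ordinarily meet an SAE criterion. TIA appears among the MAE definitions but not in the composite as worded, which is a separate inconsistency. Bleeding is the main case.
- **Attribution can err both ways.** A mixed event judged mainly due to ablation is filed wholly under ablation. This stands for attribution. It does not stand for entry: an unentered qualifying event can only lower the count.

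**Conclusion.** The point holds in a limited form. Section 7.4 has no contributory question for the ablation procedure, although relatedness to that procedure defines the primary safety composite and part of the secondary SAE endpoint. Section 7.5.1 contradicts itself on what is entered. Under its restrictive sentence, non-serious candidate MAEs, chiefly bleeding, can stay outside the adjudicator's view.

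The size is unknown, because the documents give no rate for such events. If they occurred in 1 to 2% of subjects and went unentered, the chance of passing at a true 15% rate would be at most 9.4 to 16.6% instead of 4.9%. At the expected 8.5% rate the test already passes about 79% of the time, so the exposure matters mainly if the true rate is near the goal. It is worth correcting because the pass limit is a single count, 15 of 150, and the correction is cheap.

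**What to change.** **Section 7.4.** Record relatedness separately for the device, the ablation procedure, general cardiac surgery and medication, in place of one primary cause. State that the safety endpoints use the adjudicator's relatedness.

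**Section 7.5.1.** Reconcile the two capture sentences. Require that every event within 30 days that meets the clinical criteria of a Section 4.1 MAE, leaving relatedness aside, is entered and adjudicated whatever the site's attribution or seriousness. Say how this requirement stands to the Section 7.6 list.

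**Cost.** A small set of eCRF fields and a few protocol sentences. The 30-day data come from chart review and an adjudicator is already in place. Sites will have more bleeding and transfusion events to enter, the adjudicator will have more to review, and the MAE rate may come out slightly higher.
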